3.0 Intervention to be studied

Specifically, in the 510(k) cleared Dermabond PRINEO skin closure system (Ethicon Inc.), the 2-octyl cyanoacrylate adhesive is used in combination with a polyester mesh tape, either 22cm or 60cm in width. This mesh tape is designed to provide for tighter sealing of the incision and may further protect against discharge in more mobile wounds. Use of the tape may strengthen the wound closure and also simplify and improve alignment and apposition of wound edges [[12] and Ethicon internal testing]. Several prospective randomized, controlled trials have demonstrated consistently lower wound closing times and equivalent or significantly improved cosmetic outcomes and complication rates with this system [13-16]. More flexibility in application due to “body-contouring” has also been noted [17].

Observational studies of the PRINEO system report success use of the device as evaluated by surgeon and patient satisfaction [11, 17, 18]. Research of the PRINEO system used after total joint replacement are at present limited to retrospective studies [11, 18] and case reports of allergic reactions [19, 20].

[name] currently closes incisions after shoulder arthroplasty with metal staples, and [name] currently closes incisions after shoulder arthroplasty using subcuticular sutures with Dermabond. Both surgeons use interrupted deep-layer sutures. This study will consist of two parallel comparisons to these distinct control arms. The PRINEO closing method, which utilizes running deep and superficial sutures with Dermabond PRINEO, will be directly compared to each surgeon’s wound closure technique, as half of each surgeon’s patients will be randomized to the PRINEO treatment condition while the other half continue to undergo wound closure with the current technique utilized by the

surgeon. This will result in two parallel treatment arms and two distinct control arms (Fig. 1). Both surgeons have significant experience in the application of Dermabond PRINEO for wound closure.

4.0 Study Endpoints

The duration of wound closure is primary endpoint for this study. Wound closure timing outcomes will be collected in the operating room towards the conclusion of each surgery. Closure time is the time between the first stitch for closure and the completion of application of dressing to the wound. The incision length will be measured to calculate time per centimeter.

Cost per minute of operation time is another endpoint for the study. It will be conservatively approximated using existing reports of personnel capacity rates for orthopaedic surgeon. Cost-effectiveness analysis will be conducted by comparing the total cost of all wound closure materials for each technique, and a cost per minute applied to wound closure time.

Wound outcomes, both clinical and cosmetic, will be another primary endpoint for this study. Patient-centered outcomes for wound and scar evaluation will be collected at 6 weeks and 3 month postoperative appointments in clinic. These outcomes will be measured using the Modified Hollander Cosmesis Scale [14, 21], the Patient and Observer Scar Assessment Scale (POSAS) [14, 22, 23], and the Acute Inflammatory Response Evaluation (AIRE) score as described in the 2015 study by Blondeel et al [14].

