1.0 Objectives/ Specific Aims

Our study aims to compare the efficacy of a deep-layer, knotless closing method using the Dermabond PRINEO skin closure device (2-octyl cyanoacrylate adhesive glue in combination with self-adhesive polyester mesh tape) to the current practices of wound closure after total joint arthroplasty. While surgeons utilize a variety of incision closure techniques, most use a layered closure with deep fascial closure consisting of interrupted, knotted sutures combined with either staples (Figure 1) or sutures (Figure 2) for superficial closing. In this Phase 4 clinical trial, we hypothesize that the Dermabond PRINEO wound closure system with running knotless sutures for deep and superficial closure (Figure 3) will significantly reduce closure time in the operating room and achieve similar or better incision healing after shoulder arthroplasty.

Primary aims:

1.1 Aim 1: To quantify differences the time required for wound closure with the PRINEO closure method (Figure 3) and that of traditional closure methods (interrupted deep fascial suture with either subcuticular sutures and traditional Dermabond (Figure 2) or metal staples for superficial closure (Figure 1)

H_0 : There are no differences in wound closure times between PRINEO and subcuticular sutures or metal staples in time to close incisions

H_A : There are differences between PRINEO and subcuticular sutures or metal staples in time to close incisions such that staples will be significantly faster than PRINEO and PRINEO will be significantly faster than sutures.

1.2 Aim 2: To quantify differences between PRINEO and subcuticular sutures or metal staples in wound healing over three postoperative follow-up points

H_0 : There are no differences between PRINEO and subcuticular sutures or metal staples in wound healing (dehiscence and drainage) over three postop follow-up points.

H_A : There are differences between PRINEO and subcuticular sutures or metal staples in wound healing (dehiscence and drainage) over three postop follow-up points such that PRINEO demonstrates superior healing to both sutures and staples.

Exploratory Aims:

1.3 Aim 3: To quantify differences between PRINEO and subcuticular sutures or metal staples in observer-evaluated and patient-evaluated cosmetic outcomes for the surgical scar over four postoperative follow-up points

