10.0 Study Design/ Methods

Randomization will take place the morning of surgery based on a randomly organized, computer-generated order.

Patients in [name] clinic will be randomized to one of two treatment conditions for wound closure after shoulder arthroplasty: 1) deep layer closure with 0-0 vicryl interrupted sutures followed by superficial skin closure with metal staples with aquacel dressing and 2) deep layer closure with a running 2-0 unidirectional Stratafix suture followed by superficial closure with subcuticular bidirectional 3-0 Stratafix suture followed by the Dermabond PRINEO (60cm or 22cm polyester mesh and 2-octyl cyanoacrylate adhesive) with Medipore and folded 4x4 cotton gauze dressing.

Patients in [name] clinic will be randomized to one of two treatment conditions for wound closure after shoulder arthroplasty: 1) deep closure with interrupted 2-0 vicryl sutures followed by a running subcuticular bidirectional 3-0 Stratafix with Dermabond and Medipore dressing with folded 4x4 cotton gauze dressing and 2) deep layer closure with a running 2-0 unidirectional Stratafix suture followed by superficial closure with subcuticular bidirectional 3-0 Stratafix suture followed by the Dermabond PRINEO (60cm or 22cm polyester mesh and 2-octyl cyanoacrylate adhesive) with Medipore and folded 4x4 cotton gauze dressing.

The rationale for investigating the current practice of deep closure with interrupted sutures is as follows: Using running suture introduces a potential risk of wound dehiscence if the suture fails at any juncture despite the presence of the barbs. The Dermabond PRINEO represents a powerful closure mechanism that in all probability eliminates the risk of wound dehiscence regardless of the skin closure method. Therefore, using a rapid wound closure method with deep layer running sutures is now a possibility with the Dermabond PRINEO that was not available before.

Patients will not be made aware of the treatment they are randomized to until their first follow up visit or when wound dressing is removed to reveal the device used for wound closure.

At the conclusion of the surgery, the assigned wound closure technique will be implemented. The following data points to measure the primary outcome, wound closure efficiency, will be collected in the operating room:

1. Total operating time in minutes and seconds, from the first incision to the application of wound dressing.

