11.0 Data Management

Justification of sample size:

The Cohen's effect size of 0.93 corresponds to a difference of means of 7.5 minutes with a pooled standard deviation of 8 minutes. The PI has determined that a difference of 10 minutes will be the minimum significant difference for clinical and economic relevance. 5 minutes alternatively would be an irrelevant amount of time savings. Therefore, designing the investigation to detect 7.5 minutes would ensure that we would determine if 10 minutes difference exists between the different wound closure techniques.

Economically, at an estimated cost of \$30 per minute of operative time [24], this corresponds to \$300 saved per procedure. Ten fewer minutes of operative time across six consecutive shoulder arthroplasties would save an hour total of operative time, which allows for the possible inclusion of a seventh surgery in the operative room schedule.

In our study, differences in time to closure between the groups will be compared by two-sample T-tests for independent means. With a Cohen's effect size of 0.93, a standard

alpha of 0.05 to determine statistical significance, and a target power of 0.80, an apriori power analysis indicates 76 total for the sample size, or 19 per group. A sample size of 88 total patients, with 22 in each group (two parallel treatment arms and two distinct control arms each representing surgeon's choice), will ensure sufficient power to detect economically relevant, statistically significant differences in time to closure outcomes between the three wound closure methods, while leaving room to accommodate patients who withdraw from the study or are lost to follow up.

Data storage and management:

As multiple data points will be collected for each patient over the course of their treatment, an enrollment log will be established, assigning patients unique identifiers, and a data sheet will be started where the total operating time, the wound closure time, the cost of wound closure, and the incision length will be recorded. Furthermore, the mHCS score, the AIRE score, the POSAS scores, and complications will be recorded in this data sheet for each postoperative visit to the clinic (at 6 weeks and 3 months).

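### Section 4 makes cosmetic wound outcomes part of a primary endpoint while Aim 3 makes them exploratory, and nothing controls error across scales, visits or endpoints

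*Combined protocol and SAP*

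**What the plan says.** Four places in the combined protocol and SAP bear on the status of cosmetic outcomes.

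- **Section 4.0, Study Endpoints.** It first says "The duration of wound closure is primary endpoint for this study", and later "Wound outcomes, both clinical and cosmetic, will be another primary endpoint for this study". The wound outcomes are to be measured by mHCS, POSAS and AIRE at 6 weeks and 3 months.
- **Section 1.0, Objectives/Specific Aims.** Closure time (Aim 1) and wound healing (Aim 2) are the primary aims. Aim 2 reads "To quantify differences between PRINEO and subcuticular sutures or metal staples in wound healing over three postoperative follow-up points", and its hypotheses define healing as dehiscence and drainage. Aim 3 comes under the heading "Exploratory Aims" and covers "observer-evaluated and patient-evaluated cosmetic outcomes for the surgical scar over four postoperative follow-up points".
- **Section 10.0, Study Design/Methods.** The primary outcome is singular: "The following data points to measure the primary outcome, wound closure efficiency".
- **Section 11.0, Data Management.** The sample size is justified as giving "sufficient power to detect economically relevant, statistically significant differences in time to closure outcomes", with no calculation for any wound or scar score. The data analysis plan tests mHCS, AIRE and POSAS by ANOVA followed by Tukey-HSD. It names no primary scale or visit, no order of testing and no division of alpha.

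**The concern.** The same cosmetic scores have two incompatible standings in the current text. A reader who follows Section 4.0 may treat a significant scar score as success on a primary endpoint. A reader who follows Section 1.0 must treat it as exploratory. Nothing elsewhere decides between them, so the choice could be made after the results are known.

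The stakes are practical. Aim 3 carries a directional hypothesis that PRINEO is cosmetically superior to both comparators, and Section 2.0 gives patients' satisfaction with a visible scar as a reason for the trial. A cosmetic claim is therefore one the trial would naturally want to make. Under Section 4.0 it could rest on whichever scale and visit happened to give a small p-value.

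**Working it through.** **1. Status of each outcome, side by side**

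| Outcome | Section 1.0 | Section 4.0 | Section 10.0 | Sample size, Section 11.0 |
|---|---|---|---|---|
| Closure time | primary (Aim 1) | primary | the single primary outcome | sole basis |
| Clinical wound healing | primary (Aim 2) | primary | not named as primary | not used |
| Cosmetic outcomes | exploratory (Aim 3) | primary | not named as primary | not used |

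Sections 1.0 and 4.0 conflict only in the last row.

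**2. The plan's own figure**

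Inputs from Section 11.0: difference 7.5 min, SD 8 min (7.5/8 = 0.9375, stated as 0.93), alpha 0.05, power 0.80. The plan does not state sidedness; I take it as two-sided.

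n per group = 2(z₀.₉₇₅ + z₀.₈₀)²/d² = 2(1.960 + 0.842)²/0.93² = 15.70/0.8649 = 18.15, rounded up to 19. Four groups give 4 × 19 = 76, as stated. The noncentral t gives 19 per group at d = 0.9375 (power 80.3%) and 20 at d = 0.93. The figure reproduces, and it concerns closure time only.

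**3. Number of cosmetic tests**

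The scar scales are mHCS and POSAS. AIRE is an inflammation score and is left out. Sections 4.0, 10.0 and 11.0 schedule the scales at two visits; Aim 3 speaks of four, but I use the two. I count one ANOVA per score and visit.

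- POSAS as one score: 2 scales × 2 visits = 4 tests.
- POSAS patient and observer parts separately: 3 scores × 2 visits = 6 tests.

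The plan does not say which applies. The blinded photographic POSAS rating in Section 10.0 could add more tests and is not counted.

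**4. Chance of at least one false positive, independent tests**

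The plan states no alpha for the scales; 0.05 per test is an assumption.

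- 4 tests: 1 − 0.95⁴ = 18.5%
- 6 tests: 1 − 0.95⁶ = 26.5%

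**5. The same, with correlated tests**

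Scores on the same scar are likely to be correlated, but the documents give no correlation. I simulated equally correlated standard normal test statistics (300,000 draws per setting, two-sided 0.05), a simplification of the planned ANOVAs:

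| Assumed correlation | 4 tests | 6 tests |
|---|---|---|
| 0.3 | 17.4% | 24.0% |
| 0.5 | 15.6% | 20.7% |
| 0.7 | 13.0% | 16.5% |
| 0.8 | 11.4% | 13.9% |

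Every value exceeds 5%.

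**6. If cosmetic outcomes really were a second primary endpoint**

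With alpha split 0.025/0.025, closure-time power at d = 0.93 with 22 per group (noncentral t) falls from 85.4% to 77.3%, below the 80% target. Reaching 80% would take 24 per group, or 4 × 24 = 96 in total. If cosmetic outcomes are exploratory, closure time keeps its alpha of 0.05, and 76 and 88 stand.

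**The case against.** The strongest reply is that the intended lead endpoint is plain: Section 10.0 names one primary outcome, and the trial is sized on closure time alone. On this view the sentence in Section 4.0 is loose drafting. That supports treating cosmetic outcomes as exploratory, but it does not remove a current sentence that calls them primary.

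A second reply is that the plan has some error control. This stands in part: Tukey-HSD controls the pairwise group comparisons within one scale at one visit. A reader might infer that there is no control at all, and the analysis plan does not support that. The gap is across scales, visits and endpoints.

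Two other stronger readings should be resisted.

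- **A larger error rate.** Counting AIRE with mHCS and both POSAS parts at two visits gives 8 tests and 1 − 0.95⁸ = 33.7%; adding two closure-time tests gives 1 − 0.95¹⁰ = 40.1%. AIRE measures inflammation, so these are not counts of cosmetic tests. Both figures also assume independence, which is doubtful for ratings of the same wound.
- **Closure time as the only primary endpoint.** A reader might infer from Section 10.0 that clinical wound healing should also lose primary status. Sections 1.0 and 4.0 agree that it is primary, so this contradiction gives no ground for demoting it.

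**Conclusion.** The point holds for cosmetic outcomes only. Section 4.0 gives them a primary standing that Aim 3 denies, and the analysis plan has no rule that would make a primary cosmetic claim safe. If Section 4.0 is followed, the chance of at least one false-positive scar result is 18.5% to 26.5% under independence, and about 11% to 24% at correlations of 0.8 to 0.3. These figures rest on three assumptions: 0.05 per test, two visits with 4 to 6 tests, and correlations that the documents do not supply. The contradiction itself rests on none of them.

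The sample size is not in error. The change should be made, because what the trial may claim depends on which section is followed.

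**What to change.** Reword the wound-outcome sentence in Section 4.0 so that the cosmetic scores (mHCS and POSAS) are exploratory, in line with Aim 3. State there or in the data analysis plan that their p-values are nominal. Leave clinical wound healing with the primary status it has in Sections 1.0 and 4.0, and describe it by dehiscence and drainage, as Aim 2 does, so that the scar scales no longer stand in for it.

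This takes a sentence or two. The sponsor gives up a primary cosmetic claim, and 76 and 88 are unchanged. If the sponsor wants to keep that claim, the alternative is to prespecify the scale, visit and comparison, with either a fixed testing order after closure time (sample size unchanged) or a split of alpha. An equal split would need 96 patients to hold 80% power for closure time.

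The rewording settles cosmetic outcomes only. How the two remaining primary aims relate, and how Section 10.0's single primary outcome fits with Aim 2, are separate matters.

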5.0 Inclusion and Exclusion Criteria/ Study Population

All adult (18 and older) patients undergoing primary total shoulder arthroplasty by [name] or [name] will be considered for the study. Patients will be included if they are willing and have the capacity to provide informed consent, and if they expect to continue their post-operative follow up care with their operating surgeons at MUSC.

Subjects will be excluded if:

- They have a unique, identifying tattoo or skin marking within 2 inches of intended site of surgical incision
- They self-report a known hypersensitivity to cyanoacrylate, formaldehyde, benzalkonium chloride, or pressure sensitive adhesive;
- They self-report or have a documented prior ipsilateral shoulder arthroplasty or other open ipsilateral shoulder surgery utilizing the delto-pectoral approach;

- Their medical record shows that they are HIV positive or otherwise immunocompromised;
- Their medical record shows a skin abnormality or dermatological condition which affects skin healing;
- They report a personal or family history of significant keloid or significant hypertrophic scar formations, or other problems with wound healing.

6.0 Number of Subjects

A total of 88 patients, with 22 in each treatment group, will be enrolled. With a treatment and control arm for each surgeon, this results in a total of 44 patients in a treatment arm and 44 in a control.

7.0 Setting

All research will be conducted at sites within the Medical University of South Carolina (MUSC) in Charleston, SC

8.0 Recruitment

Only patients of the treating physicians ([name] and [name]) who are indicated for total shoulder arthroplasty and meet all inclusion and exclusion criteria will be recruited. The treating physicians (either [name] or [name]) will determine eligibility based on the indication for surgery and the patient's medical history. Recruitment restricted to the surgeons' patient base only.

9.0 Consent Process:

After patient's eligibility is confirmed, patients will be approached by either the treating physician or other study staff to obtain informed consent. The consent process will take place in their private clinic room.

There will be no dedicated waiting period between informing the subject of the study and obtaining consent. Patients who express interest in participating will then review the consent document with a member of the research team, who will explain the study and answer any questions that the patient has. They will be told that by signing they understand and are agreeing to the nature of the study but that consent is voluntary and can be withdrawn at any time. To ensure proper understanding, patients will be asked to summarize main components of the study, e.g. types of data collected and post-operative clinic visits. HIPAA authorization will be obtained with informed consent.

Once the patient signs consent he/she will be given a copy of the signed form for his/her records.

10.0 Study Design/ Methods

Randomization will take place the morning of surgery based on a randomly organized, computer-generated order.

Patients in [name] clinic will be randomized to one of two treatment conditions for wound closure after shoulder arthroplasty: 1) deep layer closure with 0-0 vicryl interrupted sutures followed by superficial skin closure with metal staples with aquacel dressing and 2) deep layer closure with a running 2-0 unidirectional Stratafix suture followed by superficial closure with subcuticular bidirectional 3-0 Stratafix suture followed by the Dermabond PRINEO (60cm or 22cm polyester mesh and 2-octyl cyanoacrylate adhesive) with Medipore and folded 4x4 cotton gauze dressing.

Patients in [name] clinic will be randomized to one of two treatment conditions for wound closure after shoulder arthroplasty: 1) deep closure with interrupted 2-0 vicryl sutures followed by a running subcuticular bidirectional 3-0 Stratafix with Dermabond and Medipore dressing with folded 4x4 cotton gauze dressing and 2) deep layer closure with a running 2-0 unidirectional Stratafix suture followed by superficial closure with subcuticular bidirectional 3-0 Stratafix suture followed by the Dermabond PRINEO (60cm or 22cm polyester mesh and 2-octyl cyanoacrylate adhesive) with Medipore and folded 4x4 cotton gauze dressing.

The rationale for investigating the current practice of deep closure with interrupted sutures is as follows: Using running suture introduces a potential risk of wound dehiscence if the suture fails at any juncture despite the presence of the barbs. The Dermabond PRINEO represents a powerful closure mechanism that in all probability eliminates the risk of wound dehiscence regardless of the skin closure method. Therefore, using a rapid wound closure method with deep layer running sutures is now a possibility with the Dermabond PRINEO that was not available before.

Patients will not be made aware of the treatment they are randomized to until their first follow up visit or when wound dressing is removed to reveal the device used for wound closure.

At the conclusion of the surgery, the assigned wound closure technique will be implemented. The following data points to measure the primary outcome, wound closure efficiency, will be collected in the operating room:

1. Total operating time in minutes and seconds, from the first incision to the application of wound dressing.
2. Total time for wound closure in minutes and seconds, from the first stitch for closure to the application of wound dressing.
3. The incision length in centimeters

4. The cost of materials utilized for wound closure (suture, Dermabond, PRINEO, staples, dressings, etc.)

All patients will be seen in clinic 2 weeks post operatively during which time the wound closure technique (sutures, or staples) will be removed by a nurse according to the manufacturer and standard technique. The patients who are randomized to Dermabond PRINEO will be instructed to keep their polymer mesh on for an additional 2 weeks after their 2 weeks visit. Any complications such as drainage, acute inflammation, or signs of infection will be recorded at this time and treated per clinical standards. The following data points to measure wound clinical and cosmetic outcomes, will be collected at 6 weeks and 3 months postoperatively:

1. mHCS score
2. AIRE score
3. POSAS score
4. Complications and adverse events

mHCS, AIRE, and POSAS scores are all dependent on aspects of the physical exam, such as evaluation of pliability, temperature, edema, pain, and contour. To mitigate any observer bias, all incisions will be photographed and additionally evaluated by a plastic surgeon ([name]) blinded to the treatment condition using the POSAS-Observer characteristics which may be assessed through standardized photography alone (Vascularity, Pigmentation, Thickness, Relief, Surface Area, and Overall Opinion).

A medical record review will also be performed to collect the following data: Age; gender; BMI (including height and weight), race, diabetes status (type, insulin dependency, years diagnosed); history of smoking/tobacco use; frequency of alcohol consumption.

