H_0 : There are no differences between PRINEO and subcuticular sutures or metal staples in cosmetic outcomes over four postop follow-up points.

H_A : There are differences between PRINEO and subcuticular sutures or metal staples in wound healing (dehiscence and drainage) over four postop follow-up points such that PRINEO demonstrates superior cosmetic outcomes to both sutures and staples.

1.4 Aim 4: To quantify differences between PRINEO and subcuticular sutures or metal staples in complication rates (defined as allergic reaction, inflammation, irritation, drainage, or infection)

H_0 : There are no differences between PRINEO and subcuticular sutures or metal staples in wound complication rates over four postop follow-up points.

H_A : There are differences between PRINEO and subcuticular sutures or metal staples in wound complication rates.

1.5 Aim 5: To evaluate the overall cost-effectiveness of PRINEO for wound closure relative to subcuticular sutures and metal staples

H_0 : There are no differences between PRINEO, subcuticular sutures, and metal staples in cost-effectiveness over four postop follow-up points.

[figure not shown]
H_A : There are differences between PRINEO, subcuticular sutures, and metal staples in cost-effectiveness such that staples are superior to PRINEO and PRINEO is superior to subcuticular sutures.

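### Complications seen at the 2-week visit, the only named visit with the PRINEO mesh on, are recorded but not listed for the data sheet behind Aims 2 and 4

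*Combined protocol and SAP*

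**What the plan says.** All patients attend clinic at 2 weeks (Section 10.0). Staples or sutures are dealt with then, while PRINEO patients "will be instructed to keep their polymer mesh on for an additional 2 weeks after their 2 weeks visit". Of the same visit the section says: "Any complications such as drainage, acute inflammation, or signs of infection will be recorded at this time and treated per clinical standards". Section 14.0 makes it the occasion for a close check for irritation, blistering and inflammation. Section 12.0 has adverse events collected at follow-up visits, without listing or excluding any.

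The schedule for the scores, complications and adverse events comes next in Section 10.0: these "will be collected at 6 weeks and 3 months postoperatively". Section 4.0 gives the same timing for the wound and scar scales, including "the Acute Inflammatory Response Evaluation (AIRE) score": they "will be collected at 6 weeks and 3 month postoperative appointments in clinic". Section 11.0 then describes the data sheet: the three scores and "complications will be recorded in this data sheet for each postoperative visit to the clinic (at 6 weeks and 3 months").

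Two aims depend on these records. Primary Aim 2 compares "wound healing (dehiscence and drainage) over three postop follow-up points". Exploratory Aim 4 compares "complication rates (defined as allergic reaction, inflammation, irritation, drainage, or infection"), and its null hypothesis refers to four follow-up points. Section 11.0 assigns Chi-square tests to complication rates but does not say which visits contribute.

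**The concern.** The plan records complications at week 2 but does not carry that record into the data sheet. Section 11.0 puts the analysis covariates in the same sheet, so the sheet is evidently the source for analysis. An event present at week 2 and gone by week 6 therefore has no listed route into the comparisons of Aims 2 and 4.

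This matters because week 2 is the one named visit at which the PRINEO device is still on the skin, and it is an early time to look for drainage in every arm. If the rule is applied literally, those events are lost. If it is treated as a slip, someone decides whether they count, possibly after seeing the data by arm. Clinic staff will know the closure method by then. The blinded photographic review covers only some observer scar items, so it cannot replace a complication record.

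**Working it through.** **The plan's own figure.** The only calculated figure is the closure-time sample size. With effect size 0.93, two-sided alpha 0.05 and power 0.80, the normal approximation gives 2 × (1.960 + 0.842)² / 0.93² = 18.2, rounded up to 19 per group, and 4 × 19 = 76. This reproduces Section 11.0. The present point does not depend on it.

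**Timeline** (Sections 10.0 and 11.0), assuming patients follow the mesh instruction:

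- Mesh off: 14 + 14 = 28 days after surgery.
- 6-week visit: day 42, which is 42 − 28 = 14 days after mesh removal.
- 3-month visit: 3 × 365.25 / 12 / 7 = 13.0 weeks, which is 13.0 − 4 = 9.0 weeks after removal.

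| Named visit | Mesh on? | Complications recorded (Section 10.0) | Complications listed for data sheet (Section 11.0) | AIRE scheduled |
|---|---|---|---|---|
| 2 weeks | yes | yes | no | no |
| 6 weeks | no | yes | yes | yes |
| 3 months | no | yes | yes | yes |

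The data sheet lists 2 of the 3 named visits, and 0 of those 2 fall within mesh wear. Aim 2 needs three points. Adding week 2 supplies exactly three.

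**Content at week 2.** The week-2 sentence gives drainage, acute inflammation and signs of infection as examples. It does not name irritation or allergic reaction (both in Aim 4) or dehiscence (Aim 2). The data sheet has no separate item for dehiscence either. Even if week-2 notes are brought in later, they need not have been taken in the same way for each component.

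**How many events.** The only rate in the documents is 0% to 1.8% for allergic reaction (Section 14.0). In 44 PRINEO patients that is 0 to 44 × 0.018 = 0.79 expected reactions over all follow-up, so allergy alone is a small part. No rate is given for drainage, dehiscence, irritation, inflammation or infection. As an assumption only, if 1%, 5% or 10% of the 88 patients have a week-2 complication that resolves by week 6, then 88 × 0.01 = 0.9, 88 × 0.05 = 4.4 or 88 × 0.10 = 8.8 patients are affected. Spread evenly, each surgeon's comparison (22 against 22) would have half of that: 0.4, 2.2 or 4.4.

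**The case against.** The best answer is that this is a drafting slip. Section 11.0 speaks of every postoperative clinic visit, which ordinarily includes week 2. The bracketed times may simply repeat the schedule of the scores in the same sentence. Aim 2's three points match the three named visits. Section 12.0 excludes no visit from adverse-event collection, and Section 11.0 mentions visit report and adverse event forms. The study outline figure is not shown and some aims mention four points, so a further visit cannot be ruled out. All of this stands, and it makes it likely that week 2 was meant to count. But the bracket is the only statement of which visits feed the sheet, and nothing says that the week-2 record or the forms enter Aims 2 or 4.

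Four stronger readings are tempting and not supported:

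- **That week-2 complications go unrecorded, or that care is unsafe.** Sections 10.0, 12.0 and 14.0 provide for recording, monitoring and treatment.
- **That the AIRE schedule is an error.** Sections 4.0, 10.0 and 11.0 agree on 6 weeks and 3 months, and no aim says AIRE is to measure reaction to the mesh in place. Section 10.0 makes the scores depend on physical examination. With the mesh covering the PRINEO incision at week 2, comparable scoring across arms is not established.
- **That the omission favours PRINEO.** Lost reactions to the mesh would favour it, but lost early drainage could favour either arm.
- **That a definite amount of power is lost.** The documents give no complication rates from which to calculate it, and Section 6.0 on the size of the arms and Section 3.0 on two parallel comparisons imply 22 against 22 for each, on an exploratory aim.

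**Conclusion.** The point holds as an inconsistency between Sections 10.0 and 11.0 that affects which events are analysed. Complications are recorded at the only named visit during mesh wear, but the stated data-sheet visits leave that visit out. Taken literally, the rule excludes early events that resolve by week 6 from primary Aim 2 and exploratory Aim 4. Taken loosely, it leaves their inclusion to discretion.

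The firm size is 2 of 3 named visits listed, 0 of 2 within mesh wear, and a 14-day gap from mesh removal to the first listed entry. The number of events affected is unknown; the counts above rest on assumed rates. Events that persist to week 6, or are reported then, are still captured. The conclusion assumes that the mesh instruction is followed and that the figure not shown adds no visit. Closure time, the main endpoint, and the sample size are unaffected. This is worth correcting but does not threaten the trial.

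**What to change.** In Section 11.0, give the data-sheet visits for complications as 2 weeks, 6 weeks and 3 months, and state that week-2 events count in Aims 2 and 4. At the existing 2-week visit, record a yes/no entry in all arms for each Aim 4 component (allergic reaction, inflammation, irritation, drainage, infection) and for dehiscence.

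Two additions are optional: an AIRE score at week 2, where it can be scored with the mesh in place, and a question at 6 weeks, in all arms, about events since week 2.

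No visit is added, and the mesh instruction and sample size do not change. The cost is a corrected bracket, one sentence, and a few minutes of staff time per patient. Recorded complication counts may rise in any arm.
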